4.5 Total Number of Subjects and Sites

Recruitment will end when 1050 subject are randomized.

4.6 Vulnerable Populations

While the study will not specifically target pregnant women, any pregnant women who meet eligibility criteria would be able to enroll as phototherapy is a standard of care psoriasis treatment during pregnancy. Children that meet the eligibility requirements will be able to enroll. Assent from the child and written consent from the parent or authorized legal guardian will be obtained in accordance with the provisions of Subpart D, 45 CRF 46. Prisoners, fetuses or neonates will not be included in the study.

5 Study Intervention

5.1 Description

The comparator devices are the Daavlin 7 series 3 panel narrow band phototherapy home units (with 8-12 bulbs and a smaller, flat surface with door, measuring 21" wide, 74.5" tall, and 23.5"). This unit is a class II device with a FDA 510K indication for psoriasis, vitiligo and atopic dermatitis/eczema. The unit will have a dosimetery controller, a UV sensor built in that measures the intensity of the light. This sensor will adjust the treatment time to compensate for any variation in output due to aging of the lamps or other factors.

The reference device is office based narrow band phototherapy (units typically have at least 24 bulbs in a surround structure).

5.2 Intervention Regimen

Starting dose will be based on Fitzpatrick skin type (as ascertained by the clinical practice) and will increase based on the patient's response to the treatment. The clinicians will be allowed flexibility in deviating from this regimen based on their local practice. See Appendix A for example standardized protocol.

5.3 Receipt

The home phototherapy device will, upon order from the investigators, be shipped by common carrier in a returnable packing box to the patient specified by the investigators. The unit is a single phototherapy unit that will require unpacking and minimal assembly upon receipt. Upon notification of receipt, technical assistance staff at the device supplier will contact the patient to ensure that the device was received in good order and to answer any operational questions the patient may have as is standard practice.

5.4 Storage

The home phototherapy device should be used in a private area of the home and must be near electrical service and in a place free from temperature and environmental extremes. There are no sterilization requirements for the device. The patient must wear protective eyewear during the treatment and ensure that other family members or pets are not exposed to incidental ultraviolet radiation from the device.

5.5 Preparation and Packaging

The home phototherapy device will be shipped to the patient in a re-usable shipping container that measures approximately 80" x 23" x 16". It will be packed at the manufacturer's facility in Bryan, Ohio.

The investigational plan is for provision of just one type of phototherapy device for all patients so there are no requirements for size selection, configuration, etc, which is typical of standard practice.

5.6 Administration and Accountability

The study site will provide a prescription to Daavlin for patients randomized to home phototherapy. See Appendix C for prescription template. Participants randomized to home phototherapy will receive instructions, as approved by Daavlin and the study investigators, on how to properly use the investigational devices at home. The device will be equipped with software programmed to provide treatments as prescribed by the physician. The software also will restrict the number of treatments a participant can receive based on a unique PIN system. At the conclusion of the LITE Study or upon a participant's withdrawal from the LITE Study, whichever first occurs, at the direction of the PI, Daavlin will provide home participants with a prepaid shipping label and shipping instructions for the return of the device to Daavlin. The PI and Daavlin acknowledge that not all devices provided for use in the LITE Study will be returned to Daavlin.

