3.2.3 Primary Safety Endpoints

The primary safety outcome is the proportion of patients reporting treatment-emergent adverse events. Adverse events include patient reported burns and their severity. Patients will be queried about these events immediately prior to each phototherapy treatment by the clinical staff (for patients assigned to office base phototherapy) or by the home phototherapy machine. We will also evaluate all serious adverse events regardless of their relationship to treatment. All patients will be queried about SAEs by the sites at the visit 2. Patients can spontaneously report SAEs at any point during the study.

4 Study Population and Duration of Participation

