5.7 Subject Compliance Monitoring

Compliance will be measured by evaluating the number of study treatments received. Patients receiving home phototherapy will have this recorded by the home phototherapy device. Home phototherapy treatments will be verified via software obtained from the device upon their return to Daavlin. The data obtained from the devices will be considered the primary data for analysis. Patients randomized to office based phototherapy will have their treatments entered by the site staff. It is expected that patients will receive up to 36 treatments. Patients who receive at least 29 treatments will be viewed as compliant for the purposes of sensitivity analyses.

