6.2 Study Intervention Phase Weeks 1-12

6.2.1 Week 1

- Administer NB-UVB phototherapy three times per week
- Patient reported DLQI (complete prior to first phototherapy treatment)
- Patient reported target lesion image taken prior to first treatment
- Patient reported psoriasis topical treatment
- Patient reported response to phototherapy prior to treatments. For those on office treatment, data is entered by the sites. For those on home treatment, data is recorded on the home device.
- Phototherapy session number and dose. For those on office treatment, data is entered by the sites. For those on home treatment, data is recorded on the home device

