6.5.1 Data Collection and Follow-up for Withdrawn or Early Termination Participants

Participants who withdraw consent to participate in the study will be asked to report the reason for withdrawal.

7 Study Evaluations and Measurements

The data collected in this study are all considered relevant for routine clinical care. In routine clinical care, there is some variation in which assessments are conducted and thus we will standardize assessments for the purpose of the study.

Investigator reported measures:

1. Physicians Global assessment (PGA): This is a three item measure that asks the physician or his or her designee to assess the thickness, redness, and scale of psoriasis plaques.

2. Body Surface Area (BSA): This is a measure that asks the physician or his or her designee to assess the body surface area affected by psoriasis using the handprint method in which the palm of the entire hand approximates 1% of the body surface area. To do this, the patient's handprint, including the entire area of the palm and all 5 digits with the fingers close together but not overlapping, is used as a guide to estimate 1% of the BSA

3. Number of phototherapy treatments and dose received: This data is routinely collected in clinical practice. It will be reported by the sites for patients receiving office treatment and will be obtained from the machines for those receiving home based treatment

- 4. Copay for office-based phototherapy
- 5. Concomitant treatment

Patient reported measures:

1. Dermatology Life Quality Index: (DLQI): DLQI is a 10 item survey that asks patients questions about their health related quality of life on a 0-3 scale. DLQI is routinely used in clinical trials of psoriasis treatments and can also be used routinely in clinical practice.

2. Patient reported response to phototherapy: This is a standard question asked to the patient to document the degree and duration of erythema induced by the prior phototherapy treatment session. It is standard of care.

- 3. Patient reported time spent on travel, cost of travel, and time spent on phototherapy
- 4. Patient reported concomitant psoriasis topical treatment

5. Photograph of target psoriasis lesion (at a subset of study sites)

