8.4.3 Safety Analysis

The primary safety outcome is the proportion of patients reporting treatment-emergent adverse events. Adverse events include patient reported burns and their severity. We hypothesize that safety of home based UVB phototherapy will not be different from office based phototherapy. We anticipate based on extensive experience, that the number of clinically significant burns (i.e., which may require the patient to seek advice from the treating physician and occur due to human error) will be rare (affecting <1% of patients) and typically can be managed at home with over the counter remedies.

As ultraviolet light does not have adverse effects beyond the skin, our stakeholders believe that safety assessments should focus on skin related events such as burns and serious adverse events. We will summarize the number, severity, and type of adverse events experienced by patients in each treatment arm. We will compute the proportion of patients experiencing adverse events by treatment arm, with 95% CI. Similar to analyses for our effectiveness outcomes, we will also fit skin type-adjusted logistic regression models and use standardization to estimate adjusted risk differences between treatment arms. In addition to pooled safety analyses, we will also compare the proportion of patients experiencing adverse events between office-based and home-based phototherapy arms within each skin type sub-group

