9.2 Recording of Adverse Events

This pragmatic trial will be evaluating the effectiveness of two standard of care treatments, home and office-based phototherapy. All treatments will be administered and monitored by the patient's clinical care provider (dermatologist) and designated staff (typically phototherapy nurses). Recording of reported adverse events will be completed by the patient's clinical care provider(s) prior to the administration of each treatment (3 times per week) and the clinical course of each event will be followed until resolution, stabilization, or until it is determined that phototherapy is not the cause. Adverse events will be documented in the patient's medical record by the clinical care provider(s) throughout the 12 week intervention period and the subsequent 12 week observation period per local practice or medical center requirements. Only phototherapy-emergent adverse events will be abstracted from medical records and/or home phototherapy equipment and recorded for study objective purposes.

Serious adverse events will be recorded and monitored by the patient's clinical care provider(s), per standard of care practices, and will also be recorded, tracked, and reported by the study in the appropriate case report form and SAE reporting form at Visit 2. Serious adverse events that are identified at the end of the study intervention period will be followed up to determine the final outcome. Any serious adverse event that occurs after the study intervention period and is considered to be possibly related to the study intervention or study participation will be recorded and reported immediately.

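### Home-arm burn, session and dose data depend on device return, which the plan concedes will be incomplete, and the safety analysis has no rule for a patient without a device log

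*Combined protocol and SAP*

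**What the plan says.** The primary safety outcome is the proportion of patients with treatment-emergent adverse events, including burns and their severity (Section 3.2.3). Patients are asked about burns "immediately prior to each phototherapy treatment by the clinical staff (for patients assigned to office base phototherapy) or by the home phototherapy machine".

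The records then follow different paths. Office responses, session numbers and doses are entered by the sites. Section 6.2 says of the rest: "For those on home treatment, data is recorded on the home device". Section 7 says that treatment number and dose "will be obtained from the machines for those receiving home based treatment".

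On retrieval, Section 5.7 states: "Home phototherapy treatments will be verified via software obtained from the device upon their return to Daavlin". It adds: "The data obtained from the devices will be considered the primary data for analysis". Section 5.6 acknowledges that "not all devices provided for use in the LITE Study will be returned to Daavlin".

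On analysis, Section 8.4.3 states: "We will compute the proportion of patients experiencing adverse events by treatment arm, with 95% CI". It adds a skin-type-adjusted risk difference. It does not define the denominator or say how a home patient without a device log is handled. Section 8.4.5 covers the two primary effectiveness outcomes and the secondary and exploratory longitudinal outcomes. It does not name safety, and its tipping-point sentence does not say which outcomes it covers.

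**The concern.** A device that stays with the patient may take that patient's burn responses, session count and doses with it. No office patient can lose data this way. The trial compares home with office treatment, and Section 1.1 cites uncertainty about the safety of home units as a reason for reluctance to prescribe them. A difference between arms in how burns are captured therefore bears directly on the safety question.

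Section 8.4.3 hypothesises no safety difference. If home treatment did cause more burns and some went unrecorded, the comparison would move towards that hypothesis. Home adherence and dose are exposed to the same loss, although the consequence there can run the other way.

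**Working it through.** **Step 1. Where each item can be captured**

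| Item | Office | Home |
|---|---|---|
| Burn response before each session | Asked by staff, entered by site | Asked by and recorded on the device |
| Session number and dose | Entered by site | Recorded on the device; treatments verified on return |
| Significant reaction | Patient contacts clinician (7.6) | Same |
| Serious adverse event | Site asks at visit 2 (3.2.3) | Same |
| Adverse event in medical record | Abstracted (9.2) | Abstracted, but no provider is present at the session |
| Items listed for the four-weekly schedule (6.2, 6.3) | No burn item | No burn item |

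No remote upload or interim download is described. What could be lost is therefore mainly milder burns, session counts and doses.

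**Step 2. Inputs**

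The plan has no figure of its own on this point to reproduce.
- Share of devices not returned, r: not given; assumed 10–20%.
- True home burn proportion, p: not given. Section 1.2.3 cites mild erythema of 10% (2 of 20) and 15% (13 of 79 as printed; 13/79 is 16.5%). Both are paediatric and clinic-based, so 10–15% is a stand-in.
- Share of the affected burns caught by another route, c: unknown; 0, 50% and 90% shown.

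**Step 3. Patients without a log counted as event-free**

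If burn rates are equal in returners and non-returners, shift = −p × r × (1 − c).

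| p | r | c = 0 | c = 50% | c = 90% |
|---|---|---|---|---|
| 10% | 10% | −1.0 | −0.5 | −0.1 |
| 10% | 20% | −2.0 | −1.0 | −0.2 |
| 15% | 10% | −1.5 | −0.75 | −0.15 |
| 15% | 20% | −3.0 | −1.5 | −0.3 |

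Entries are percentage points. Using 16.5% in place of 15% moves the largest entry to 0.165 × 0.20 = 3.3 points. For clinically significant burns, which Section 8.4.3 expects in under 1% of patients, the shift is at most 0.01 × 0.10 = 0.1 to 0.01 × 0.20 = 0.2 points.

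**Step 4. Patients without a log excluded**

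Let k be the burn rate in non-returners divided by that in returners. Shift = p / ((1 − r) + r × k) − p. At p = 10%, r = 20%:
- k = 0.5: 0.10/0.90 − 0.10 = +1.1 points (against home)
- k = 1: 0
- k = 2: 0.10/1.20 − 0.10 = −1.7 points (favours home)
- k = 3: 0.10/1.40 − 0.10 = −2.9 points (favours home)

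The sign depends on a handling rule that the plan does not state and, under exclusion, on a ratio that nobody knows.

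**Step 5. Scale**

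The 95% half-width of a risk difference is 1.96 × √(2p(1 − p)/n). At p = 10% it is 3.6 points with 525 per arm (1050/2). With 390 per arm (350 + 350 + 80 = 780, halved; Section 3.1) it is 4.2 points. The shifts in Step 3 are smaller than this, but a larger sample would not reduce them.

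**Step 6. Counts and dose**

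Section 5.7 calls at least 29 of 36 treatments (80.6%) compliant, and Sections 8.4.4 and 8.5 use an 80% as-treated set. If a missing log were scored as zero sessions, the home compliant proportion would fall by r times the true compliance of non-returners. That is between 0 and 10 points at r = 10%, and between 0 and 20 points at r = 20%. This runs against home.

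**The case against.** The strongest reply is that the device is not the only source of adverse events. Section 9.2 says: "Only phototherapy-emergent adverse events will be abstracted from medical records and/or home phototherapy equipment and recorded for study objective purposes". Patients are told to contact clinicians about significant reactions (7.6), site personnel review patient-reported responses and document events (Section 9), and sites ask every patient about serious events at visit 2. This largely stands for significant and serious events. It is weaker for milder burns: no provider is present at a home session, no route is described by which sites see home responses before return, and the visit-2 question covers serious events only.

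Section 5.6 is an accountability statement and gives no rate. The documents do not say whether logs can be read without return. Appendix E lists a phototherapy response questionnaire and Appendix F the data safety plan, but neither text is available here, so a second patient-reported source cannot be excluded.

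Dosing is named among the outcomes for multiple imputation when more than 10% of observations are missing (8.4.5). That stands, with a limit. If office data are complete and the arms contribute equally, home non-return of 10–20% makes 5–10% of all observations missing, which does not exceed the trigger.

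A reader might infer that safety data are missing in the home arm alone. The documents do not support this. Only non-return is confined to home. A burn after the last session, or one that ends treatment, escapes the pre-treatment question in both arms, and office data depend on site entry.

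**Conclusion.** The point holds as a gap in ascertainment and in the analysis rules. Capture of the primary safety outcome differs by arm, mainly for milder burns, and the plan gives neither a safety denominator nor a rule for a missing log.

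The direction of bias is undetermined. It favours home if patients without a log count as event-free, or if they are excluded and non-returners burn more. Under exclusion it can be zero or reversed. Under the assumptions of 10–20% non-return and 10–15% mild erythema, the understatement is about 1–3 points in the event-free case with nothing caught elsewhere, and less with other capture.

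A reader might infer a definite bias in favour of home, because Section 8.5 bases the primary analysis on all randomised subjects and an absent record looks like no event. No written rule says so, and Section 8.4.3 does not adopt that denominator. A reader might also assume event rates of 20–40% and reach 0.10 × 0.20 = 2 to 0.20 × 0.40 = 8 points. The documents give no such rates.

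This should be corrected. It does not by itself undermine the effectiveness comparison.

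**What to change.** 1. In Section 8.4.3, treat home patients without a device log as missing unless an event is documented elsewhere: neither event-free nor zero treatments. Define the safety denominator, report the share missing by arm, and name the primary safety outcome in the tipping-point analysis of Section 8.4.5. Apply the same missing-not-zero rule to the 29-treatment and 80% classifications. State whether logs can be retrieved without return. The cost is analysis-plan wording, settled before unblinding.
2. Add one burn and severity item to the four-weekly app survey in both arms during the intervention phase, including the week-12 or end-of-treatment survey. This gives a common source that depends neither on device return nor on who asks, and it reaches burns after the last session. First check it against the questionnaire listed in Appendix E. The cost is one more question per survey. It relies on recall and does not recover counts or doses.
3. Reconcile Sections 5.6 and 5.7.1 on when devices go back. The first ties return to the end of the study or withdrawal, the second to completion of the treatment regimen.

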5.7 Subject Compliance Monitoring

Compliance will be measured by evaluating the number of study treatments received. Patients receiving home phototherapy will have this recorded by the home phototherapy device. Home phototherapy treatments will be verified via software obtained from the device upon their return to Daavlin. The data obtained from the devices will be considered the primary data for analysis. Patients randomized to office based phototherapy will have their treatments entered by the site staff. It is expected that patients will receive up to 36 treatments. Patients who receive at least 29 treatments will be viewed as compliant for the purposes of sensitivity analyses.

5.7.1 Return or Destruction of Investigational Product

The investigational device will be returned to the manufacturer upon the patient's completion of their treatment regimen and at the direction of the investigators. The device manufacturer will call the patient to provide instruction and answer any questions as to how to re-pack the device, affix the shipping label and prepare it for transportation back to the manufacturer.

6 Study Procedures (Appendix D)

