Duration of response will be measured in patients who achieved a DLQI score of 5 or less at week 12, are no longer receiving phototherapy, and who have not initiated a new systemic treatment or had dose escalation of an existing psoriasis systemic treatment at any point during the study. Duration of response will be defined as the length of time from week 12 to the earliest of DLQI > 5 or time of initiation of a new systemic treatment or dose escalation of an existing systemic treatment, with patients who maintain DLQI \leq 5 throughout the 12 week observation period with no new systemic treatments or dose escalation censored at week 24. In order to obtain results that are generalizable to the full ITT study population, we will use inverse probability weighting to account for possible selection bias due to differences between characteristics of participants included in this analysis and the full study population. Duration of response will be analyzed using a Cox proportional hazards regression model adjusted for treatment arm, skin type, and their interaction. Based on results for the interaction term between study arm and skin type, we will report differences in duration of treatment response between study arms by skin type.

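### Device-return triggers in 5.6 and 5.7.1 conflict, and phototherapy resumed in weeks 13-24 is neither collected (6.3) nor handled in the duration-of-response analysis (8.2)

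*Combined protocol and SAP*

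**What the plan says.** **Device return.** Section 5.6 has the manufacturer send the return label and instructions "At the conclusion of the LITE Study or upon a participant's withdrawal from the LITE Study, whichever first occurs", at the direction of the principal investigator. Section 5.7.1 has the device go back on the patient's "completion of their treatment regimen and at the direction of the investigators".

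**Limits on use.** Section 5.6 states: "The device will be equipped with software programmed to provide treatments as prescribed by the physician". It adds: "The software also will restrict the number of treatments a participant can receive based on a unique PIN system". The permitted number is not given. Section 5.7 gives only an expectation: "It is expected that patients will receive up to 36 treatments". Section 5.6 also accepts that "not all devices provided for use in the LITE Study will be returned to Daavlin".

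**Duration of response.** Section 8.2 restricts this analysis to patients with DLQI of 5 or less at week 12 who "are no longer receiving phototherapy" and have had no new or escalated systemic treatment. Response ends at the first of DLQI above 5, a new systemic treatment, or escalation of an existing one. Patients with none of these are censored at week 24.

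**Data in weeks 13-24.** Section 6.3 lists DLQI, a target-lesion image, topical treatment and, at week 24, oral and biologic medication. Session number and dose are scheduled in section 6.2, through week 12.

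**The concern.** There are two linked problems. First, the protocol gives two answers to when the home unit leaves the home, and does not say whether the PIN restriction stops use when the intervention phase closes.

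Second, the analysis of durability treats two kinds of re-treatment differently. Starting or escalating a systemic agent ends the response. Restarting phototherapy, the treatment under study, does not, although being off it is a condition of entry. Section 1.1 describes maintenance sessions or a later repeat course as ordinary practice, so restarts are foreseeable in both arms. With no scheduled record of them, the analyst could not reliably identify these patients.

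What is at stake is the interpretation of duration of response, a secondary endpoint that section 2.1 also names in the primary objective. The between-arm comparison of dichotomized DLQI in weeks 13-24 is also affected, because section 8.2 puts no off-phototherapy condition on it.

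**Working it through.** **1. Gap between the return triggers.** Section 4.4 gives 168 days of participation after starting phototherapy: an 84-day intervention phase and an 84-day observation phase. For a patient treated to day 84 and followed to day 168, the gap is 168 - 84 = 84 days, or 12 weeks. It is longer if the study's conclusion in 5.6 means the end of the whole trial.

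**2. The plan's own treatment counts.** 3 per week x 12 weeks = 36, matching section 5.7. Its compliance threshold of 29 is 0.80 x 36 = 28.8, rounded up.

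**3. Sessions that could remain at week 12.** Assumption: the PIN limit equals the 36 expected treatments.
- 36 used: 36 - 36 = 0 left.
- 29 used: 36 - 29 = 7 left, which is 7/3 = 2.3 weeks at three per week or 7 weeks at one per week.
- 24 used: 36 - 24 = 12 left, which is 12/3 = 4 weeks at three per week or 12 weeks at one per week.

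So even a patient classed as compliant might have sessions left, while one who used the full number would have none. If the software also closes on a date, nobody would have any.

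**4. Following one patient through section 8.2.** A patient has DLQI of 5 or less at week 12, is off phototherapy and enters the analysis. The patient restarts phototherapy at week 16 and keeps DLQI at 5 or below to week 24. No listed end event has occurred, so the patient is censored at week 24 as still responding. Had the patient started a systemic agent at week 16, response would have ended then. The inverse probability weighting in 8.2 corrects for who enters the analysis, not for treatment after entry.

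**5. Illustration of how far the comparison could move.** No input here comes from the documents. Let s be the office-arm relapse proportion over the 12 weeks and f the fraction of home patients in the analysis who resume. Suppose resuming halves their hazard throughout, there is no true difference, and nobody in the office arm resumes. Then:

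- office survival S0 = 1 - s
- home survival Sh = (1 - f) x S0 + f x S0^0.5
- apparent home:office ratio of cumulative hazards = ln(Sh) / ln(S0)

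For s = 0.50 and f = 0.25: Sh = 0.75 x 0.50 + 0.25 x 0.707 = 0.552, and ln(0.552)/ln(0.50) = 0.86.

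For s from 0.30 to 0.70:
- f = 0.10: 0.93 to 0.95
- f = 0.25: 0.84 to 0.87
- f = 0.50: 0.71 to 0.74

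If the same fraction resumed in both arms with the same effect, Sh would equal the office value and the ratio would be 1. Apparent duration would then be lengthened in both arms without a spurious difference between them.

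**The case against.** A reader might infer that home patients keep a working device throughout observation and that duration of response is therefore biased toward home. The documents do not support that.

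- **Possession is not use.** The software gives treatments as prescribed and restricts their number. Section 3.1.2 sets treatment at up to 12 weeks, and section 12.2 describes the benefit as 12 weeks of home phototherapy. A closing date may appear in the Appendix C prescription template, which is listed by title but not reproduced in the text reviewed. Whether use is possible after week 12 is unknown.
- **A one-arm effect is not shown.** Nothing in 3.1.3, 6.3 or 8.2 bars office sessions in weeks 13-24, and the maintenance remark in 1.1 is not limited to home units. A unit already at home is easier to reach than an office visit with travel and co-pays, but that makes an imbalance plausible, not established.
- **Treatment still under way at week 12 is already addressed.** The entry condition in 8.2 excludes those patients, and sessions are recorded to week 12. Only later resumption is left open.
- **Some data may exist.** Device logs are the primary record for the home arm (5.7), and a unit kept longer could log later sessions. This covers returned units only, and there is no office counterpart scheduled after week 12.
- **Counting resumption as an event is an estimand choice.** A pragmatic trial could instead measure how long DLQI stays low whatever the treatment. But 8.2 already requires patients to be off phototherapy at entry and ends response at systemic re-treatment, so its own logic points the other way.
- **A crude rule could misfire.** Section 3.1.2 assigns late starters a start at day 14 after randomization, so sessions of their original course can fall after nominal week 12. Those should not count as relapse. This stands and shapes the fix.

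**Conclusion.** Two things are established from the text. The return triggers in 5.6 and 5.7.1 conflict, about 12 weeks apart for a patient who completes, and must be reconciled. Phototherapy resumed in weeks 13-24 has no place in the duration analysis and no scheduled collection in 6.3, so a patient who restarts can be counted as still responding.

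The direction follows from the definition if resumed treatment delays relapse: apparent response lengthens. Whether it lengthens more in the home arm depends on the unstated PIN limit, any closing date, the actual return date and how many office patients resume. The size is therefore unknown. The range 0.71 to 0.95 above shows only what assumed inputs would produce, and equal resumption in both arms would give 1.

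The week-12 co-primary endpoints do not depend on any of this. The point is worth correcting because a named endpoint cannot be interpreted as the plan intends without the missing data, and the correction is cheap.

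**What to change.** 1. Reconcile 5.6 and 5.7.1 on when the device is returned. State the PIN limit and whether it ends use at the close of the intervention phase. This review takes no position on which return date or limit should apply.
2. Add phototherapy use to 6.3 for weeks 13-24 in both arms: an app item with the existing four-weekly questionnaire or a site record, supplemented by the device log where the unit is returned.
3. In 8.2, for patients who entered the duration analysis as off phototherapy, count resumed phototherapy as an end event alongside new or escalated systemic treatment. Late sessions of the original course should be handled by the existing entry condition and not counted as events.
4. Report observation-phase DLQI with a sensitivity analysis that accounts for phototherapy after week 12.

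The cost is protocol wording, one app item and one added event type, plus the sensitivity analysis. Sample size and the co-primary analyses do not change.
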